### 6.3.2. Pharmacokinetics Analyses

#### Pharmacokinetic Concentrations

The concentration-time data will be summarized by descriptive statistics (n, mean, standard deviation, coefficient of variation (CV), median, minimum, maximum, geometric mean and its associated CV) by treatment/dose, cycle, day and nominal time. In addition, the concentration-time data from Part 2 may also be summarized by descriptive statistics according to tumor type if data permit.

The concentration-time data will be presented as below:

- A listing of all concentrations by treatment/dose, subject ID, cycle, day, and nominal time post dose. The concentration listing will also include the actual times. Deviations from the nominal time will be given in a separate listing.
- A summary of concentrations by treatment/dose, cycle, day, and nominal time post dose, where the set of statistics will include n, mean, standard deviation, median, coefficient of variation (CV), minimum, maximum and the number of concentrations above the lower limit of quantification.
- Median concentration-time plots (on both linear and semi-log scales) against nominal time postdose by cohort (all cohorts on the same plot per scale, based on the summary of concentrations by cohort and time postdose).
- Mean concentration-time plots (on both linear and semi-log scales) against nominal time postdose by cohort (all cohorts on the same plot per scale, based on the summary of concentrations by cohort and time postdose).
- Individual concentration time plots by subject (on both linear and semi-log scales) against actual time postdose [there will be separate plots for each subject per scale].

For drug concentration summary statistics, median and mean plots by sampling time, the nominal PK sampling time will be used; for individual subject plots by time, the actual PK sampling time will be used.

In addition to the above, predose concentrations will be plotted for each dose using a box-whisker plot by cycle and day within cycle in order to assess the attainment of steady state.

### Pharmacokinetic Parameters

To assess the pharmacokinetics of PF-06671008, the PK parameters detailed in [Section 3.2](#) will be listed and summarized for subjects in the PK analysis set (as defined in [Section 4.4](#)). Missing values will be handled as detailed in [Section 5.4.3](#). Each PK parameter will be summarized by dose, cycle, and day and will include the set of summary statistics as specified in the table below:

Parameter	Summary statistics
$C_{\max}$ , $AUC_{\inf}$ , $AUC_{sd,\tau}$ , $CL$ (for IV), $CL/F$ (for SC), $C_{\max,ss}$ , $C_{\min,ss}$ , $AUC_{ss,\tau}$ , $V_{ss}$ (for IV), $V_{ss}/F$ (for SC) and $R_{ac}$	N, arithmetic mean, median, cv%, standard deviation, minimum, maximum, geometric mean
$t_{1/2}$	N, arithmetic mean, median, cv%, standard deviation, minimum, maximum
$T_{\max}$ , $T_{\max,ss}$	N, median, minimum, maximum

For Part 1, dose normalized  $AUC_{\text{inf}}$  ( $AUC_{\tau}$  at steady state), and  $C_{\text{max}}$  will be plotted against dose (using a logarithmic scale) by cycle and day. These plots will include individual patient values and the geometric means for each dose. These plots will be used to help understand the relationship between the PK parameters and dose.

### 6.3.3. Immunogenicity Assessment

For the immunogenicity data, the percentage of patients with positive ADAs and neutralizing antibodies will be summarized by overall, by treatment/dose and by tumor type, as data permit. For patients with positive ADAs, titer, time of onset, and duration of ADA response will also be described, if data permit. In addition, efforts will be made if data permit, as appropriate, to examine possible correlations of the ADA response with clinical data on the PK, safety and/or efficacy.

CCI

### 6.5. Population PK and PKCCI Modeling

Pharmacokinetic CCI data from this study may be analyzed using modeling approaches and may also be pooled with data from other studies to investigate any association between PF-06671008 exposure CCI or significant safety endpoints. The results of these analyses, if performed, may be reported separately.

### 6.6. ECG Analysis

The analysis of ECG results will be based on patients in the Safety Analysis Set with baseline and on-treatment ECG data, and will follow the ICH E14 guidance on the clinical evaluation of QT/QTc interval prolongation and proarrhythmic potential for non-antiarrhythmic drugs.

ECG measurements (an average of the triplicate measurements) will be used for the statistical analysis and all data presentations. Any data obtained from ECGs repeated for safety reasons after the nominal time-points will not be averaged along with the preceding triplicates. Interval measurements from repeated ECGs will be included in the outlier analysis (categorical analysis) as individual values obtained at unscheduled time points.

QT intervals will be corrected for HR (QTc) using standard correction factors [ie, Fridericia's (default correction), , and possibly a study specific factor, as appropriate]. QTcF interval will be calculated using the Fridericia formula, as follows:

$$QTcF = \frac{QT}{\sqrt[3]{RR}}$$

Data will be summarized and listed for QT, HR, RR, PR, QRS, QTcF (and/or QTcB if deemed appropriate by overall, and dose. Individual QT (all evaluated corrections) intervals will be listed by cohort, time and dose. The most appropriate correction factor will be selected and used for the following analyses of central tendency and outliers and used for the study conclusions. Descriptive statistics (n, mean, median, standard deviation, minimum, and maximum) will be used to summarize the absolute corrected QT interval and changes from baseline in corrected QT after treatment by study arm dose and time point. For each patient and by treatment, the maximum change from baseline will be calculated as well as the maximum post-baseline interval across time points. Categorical analysis will be conducted for the maximum change from baseline in corrected QT and the maximum post-baseline QT interval.

Shift tables will be provided for baseline vs worst on treatment corrected QT (one or more correction methods will be used) using maximum CTCAE version 4.03 Grade. Shift tables will also be provided for ECG abnormality at baseline vs. on treatment (yes, no, not done: (n, %)).

Patients experiencing clinically-relevant morphological ECG changes will be summarized (including frequency and percentage).

The effect of drug concentrations on corrected QT change from baseline will be explored graphically. Additional concentration-corrected QT analyses may be performed. Data may be pooled with other study results and/or explored further with PKCCI models.

Changes from baseline for the ECG parameters QT interval, heart rate (HR), QTc interval, PR interval and QRS interval will be summarized by treatment and visit. Categorical data analysis will follow [Appendix 2](#).

If more than one ECG is collected at a nominal time post dose (for example, triplicate ECGs), the mean of the replicate measurements will be used to represent a single observation at that time point. If any of the three individual ECG tracings has a QTc value  $\geq 500$  msec, but the mean of the triplicates is not  $\geq 500$  msec, the data from the subject's individual tracing will be described in a safety section of the study report in order to place the  $\geq 500$  msec value in appropriate clinical context. However, values from individual tracings within triplicate measurements that are  $\geq 500$  msec will not be included in the categorical analysis unless the average from the triplicate measurements is also  $\geq 500$  msec. Changes from baseline will be defined as the change between QTc post dose from the time-matched average of the pre-dose triplicate values on Day 1.

In addition, an attempt will be made to explore and characterize the relationship between plasma concentration and QT interval length using a PKCCI modeling approach, if data warranted. If a PKCCI relationship is found, the impact of subject factors (covariates) on the relationship will be examined.

## 7. INTERIM ANALYSES

No formal interim analysis is planned in this study. However, since this is an open-label study, safety dataCCI [REDACTED] data will be monitored.

## 9. APPENDICES

### Appendix 1. Time to Event Data Analysis Censoring Rules

**Table 3. Progression Free Survival and Duration of Response**

Situation	Date of Progression/Censoring 	Outcome
Inadequate baseline assessment	First dosing date in Cycle 1	Censored
No on-study assessments	First dosing date in Cycle 1	Censored
Alive, on treatment  and no Progression	Date of last objective tumor assessment	Censored
Progression Documented on or between scheduled tumor assessments prior to treatment discontinuation 	Date of first objective tumor assessment showing objective progression	Progressed (Event)
Treatment discontinuation for undocumented progression	Date of last objective tumor assessment prior to discontinuation 	Censored
Treatment discontinuation due to toxicity or other reason	Date of last objective tumor assessment prior to discontinuation 	Censored
Death prior to first planned tumor assessment	Date of death	Death (Event)
Death without objective progression prior to treatment discontinuation 	Date of death	Death (Event)
Death or progression after 2 or more missed tumor assessments	Date of last objective tumor assessment prior to the event	Censored

1: For date of censorship, if a tumor assessment takes place over a number of days (eg, superficial lesions one day, scans another), the last date is used as the assessment date.

2: or within 28 days of discontinuation of treatment.

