6.3. Follow-up Visit

For follow-up procedures see [Schedule of Activities](#) and [Assessments](#) section. The EOT assessments are to be obtained if they are not completed in the last week (last 6 weeks for tumor assessments). The Follow-Up visit should be conducted at least 28 days, and no more than 35 days, after discontinuation of treatment. Patient will return to undergo assessments per the [Schedule of Activities](#) and will be evaluated for the resolution of any

treatment-related toxicity. Patients continuing to experience toxicity at this point following discontinuation of treatment will continue to be followed at least every 4 weeks until resolution or determination, in the clinical judgment of the investigator, that no further improvement is expected. Subsequent to the Follow-Up visit, patients should be contacted by telephone every 8 weeks (± 7 days) to obtain information on subsequent anti-cancer treatment and overall survival for up to two years after randomization.

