**Table 4. Time to Progression**

Situation	Date of Progression/Censoring	Outcome
Inadequate baseline assessment	First dosing date in Cycle 1	Censored
No on-study assessments	First dosing date in Cycle 1	Censored
Alive, on treatment  and no Progression	Date of last objective tumor assessment	Censored
Progression Documented on or between scheduled tumor assessments prior to treatment discontinuation 	Date of first objective tumor assessment showing objective progression	Progressed (Event)
Treatment discontinuation for undocumented progression	Date of last objective tumor assessment prior to discontinuation 	Censored
Treatment discontinuation due to toxicity or other reason	Date of last objective tumor assessment prior to discontinuation 	Censored
New anticancer treatment <28 days after discontinuation of treatment without progression	Date of last objective tumor assessment prior to new anticancer treatment	Censored
Death prior to first planned tumor assessment	Start date (C1D1)	Censored
Death without objective progression prior to treatment discontinuation 	Date of last objective tumor assessment prior to death	Censored
Progression after 2 or more missed tumor assessments	Date of last objective tumor assessment prior to the event	Censored

1: For censoring date, if a tumor assessment takes place over a number of days (eg, superficial lesions one day, scans another), the last date is used as the assessment date.

2: or within 28 days of discontinuation of treatment.

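### SAP Table 3 gives some patients two PFS outcomes and censors others for reasons related to prognosis

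*SAP*

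**What the plan says.** SAP Appendix 1, Table 3 governs PFS and DOR. A note after Table 4 applies the same rules to duration of stable disease (DOSD). The rows that matter here are:

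- **Stopping treatment.** "Treatment discontinuation for undocumented progression" and "Treatment discontinuation due to toxicity or other reason" are both censored at the last objective scan.
- **Death around stopping.** "Death without objective progression prior to treatment discontinuation" is an event on the date of death. The row carries footnote 2: "2: or within 28 days of discontinuation of treatment". The documented-progression row, also an event, carries the same footnote.
- **No scan yet.** "No on-study assessments" is censored at first dose. "Death prior to first planned tumor assessment" is an event on the date of death.
- **Gap in scans.** An event that follows two or more missed scans is censored at the last scan before it.

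Table 4, for time to progression (TTP), has a row for "New anticancer treatment <28 days after discontinuation of treatment without progression". Table 3 has no such row.

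Protocol Section 7.4 ends scheduled scans at permanent discontinuation. Protocol Section 6.3 then provides telephone contact every 8 weeks to record later anticancer treatment and "overall survival for up to two years after randomization". SAP Section 5.3.1 summarises time-to-event endpoints by Kaplan-Meier, and SAP Section 5.1 states that nothing is tested. The mITT set used for PFS (SAP Sections 4.6 and 6.3.1) expressly includes patients who die before their first scan.

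**The concern.** There are two separate problems. First, the rows of Table 3 overlap and nothing says which one wins, so two programmers could derive different PFS times and event counts from the same data. Second, Kaplan-Meier assumes that a censored patient has the same outlook as those still followed. A patient taken off treatment because the disease is visibly worsening, but with no scan to prove it, does not fit that assumption. Nor is there an event row for most deaths more than 28 days after stopping, although the survival calls will capture them. Both features tend to make PFS look longer than it is. With 10 to 20 patients per indication in Part 2, one or two reclassified patients can visibly move a median.

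**Working it through.** The documents give no PFS median, event count or rate of unscanned progression, so there is no planned figure to reproduce. The check applies the rows to test patients and then asks how large the effect could be.

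**Step 1. Test patients.** Scans every 6 weeks fall on days 43, 85 and 127.

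| Patient | Censoring row | Event row |
|---|---|---|
| (a) Stable on day 43, stops for toxicity day 60, dies day 75 (15 days after stopping) | Toxicity: censored day 43 | Death with footnote 2: event day 75 |
| (b) Dies day 30, never scanned | No assessments: censored at first dose | Death before first planned scan: event day 30 |
| (c) Stops for toxicity day 60, progression on scan day 70 | Toxicity: censored (day 43, or day 70 if footnote 2 is read into the date) | Documented progression with footnote 2: event day 70 |
| (d) Stable on day 43, stops for toxicity day 60, dies day 100 (40 days after stopping) | Toxicity: censored day 43 | None |
| (e) Stops day 60, new therapy day 70, progression on scan day 84 | No new-therapy row in Table 3; Table 4 has one | Documented progression with footnote 2: event day 84 in Table 3 |

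Patients (a), (b) and (c) each have two outcomes. Pattern (b) can arise only for PFS, since DOR and DOSD require a scan. Patient (d) has one outcome, and the death is never used. Patient (e) shows the difference between the tables. It matters only when new therapy and then an event both fall within 28 days of stopping, because otherwise the discontinuation rows already censor the patient.

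**Step 2. Size, in general form.** Let the event hazard be λ and let a share f of true progressions or deaths be recorded as censored. The observed hazard is then about (1 − f)λ, and the median ln 2/λ becomes ln 2/[(1 − f)λ], a factor of 1/(1 − f). The values of f are assumed:

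- f = 20%: 1/0.80 = 1.25, or +25%
- f = 30%: 1/0.70 = 1.43, or +43%
- f = 40%: 1/0.60 = 1.67, or +67%

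**Step 3. Illustrative simulation.** There were 200,000 patients per setting. Scans are 6-weekly and stop at discontinuation. The remaining inputs are assumptions: exponential time to progression with median 12 weeks; median survival 12 weeks after stopping; 5% of events are deaths on treatment; 10–30% are clinical progression without a scan; 10–30% of patients stop for toxicity first.

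| Rule | Events per 20 patients | Median, weeks |
|---|---|---|
| Discontinuation rows win | 9.8–16.2 | 17–18 |
| Death within 28 days of stopping wins | 11.9–17.0 | 12–18 |
| All deaths to two years counted, clinical progression not | about 20 | 15–18 |
| Clinical progression and all deaths counted | about 20 | 12 |

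Setting by setting, the choice between the first two rules moves 0.8 to 2.1 events per 20 patients. The medians need care: the assumed true median of 12 weeks falls exactly on a scan date, so a modest loss of early events pushes it a whole scan interval, to 18 weeks. The table shows direction and sensitivity to the rule. It does not forecast a bias.

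**Step 4. The missed-scan row.** Move patient (d)'s death to day 140. The day 85 and day 127 scans were not done because treatment had ended. Read literally, the missed-scan row would still censor this death at day 43 even if later deaths were otherwise counted.

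**The case against.** Several points on the other side carry weight.

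- **The intended order can be inferred.** The second discontinuation row covers every remaining reason for stopping. If it always won, footnote 2 on the death row would have no effect, so the authors presumably meant the event rows to win. That supports the fix, but the table does not say it, and the no-assessment overlap has no such clue.
- **Unscanned progression is not left unaddressed.** Protocol Section 7.4 also calls for imaging when progression is suspected, and at withdrawal if none was done in the previous 6 weeks. Protocol Appendix 4 and SAP Appendix 3 ask for efforts to document progression after treatment ends. These provisions reduce f. A reader might infer that nothing after discontinuation can correct the record; the documents do not support that.
- **Toxicity stops are not hidden progressions.** A patient who stops for toxicity may be far from progressing. The factor 1/(1 − f) describes true events recorded as censored, not that whole row, and the direction of any bias from it is not established.
- **The 28-day limit may be deliberate.** It resembles an on-treatment definition of PFS, and later deaths still enter overall survival. This is a fair reason to keep the main rule, but not to omit a sensitivity analysis.
- **Little rests on PFS.** It is secondary, and the rules for stopping an indication use objective response. With 20 events, an approximate exponential 95% interval for the median runs from exp(−1.96/√20) = 0.65 to exp(1.96/√20) = 1.55 times the estimate; with 10 events, from 0.54 to 1.86. An inflation of 25% lies inside both. Listings and swimmer plots will show individual cases. A wide interval does not remove a systematic shift, however, and summaries pooled across groups would be tighter.

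**Conclusion.** The point holds, with limits. Table 3 assigns two outcomes to identifiable patients and states no precedence; that follows from the text alone. It also censors patients who stop for undocumented progression, and deaths without documented progression more than 28 days after stopping unless these precede the first planned scan. Censoring is therefore partly related to prognosis, and PFS is likely overstated.

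The amount is unknown. A figure such as +25% rests wholly on an assumed f of 20%, and scans at suspected progression or at withdrawal lower f. A reader might take the larger multipliers, or the simulated 17–18 weeks against 12, as the bias to expect; the documents contain nothing to support that. A reader might also see the missing new-therapy row as a source of material bias. It is a minor inconsistency confined to the 28-day window, and adding the row would turn some events into censored times. Type I error is not at issue, and the Part 2 primary endpoint, objective response, is unaffected.

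**What to change.** 1. State in Table 3 that the event rows take precedence over the discontinuation and no-assessment rows. The event rows are documented progression or death up to 28 days after stopping, and death before the first planned scan.
2. Keep the main rule otherwise, and add one sensitivity Kaplan-Meier analysis of PFS. It should count stopping for clinical progression as an event at the stop date, and any death not preceded by new anticancer therapy as an event at death. Both are needed: in the simulation, counting later deaths alone left the median at 15–18 weeks. The row for two or more missed scans should not apply to patients whose scans ended because treatment stopped.
3. Reconcile Tables 3 and 4 on new anticancer therapy, or state why they differ.

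The cost is SAP table edits and one further analysis, using survival and subsequent-therapy data that the protocol already collects. The sensitivity estimate of PFS will probably be less favourable than the main one.

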**Table 4. Time to Progression**

Situation	Date of Progression/Censoring	Outcome
Inadequate baseline assessment	First dosing date in Cycle 1	Censored
No on-study assessments	First dosing date in Cycle 1	Censored
Alive, on treatment  and no Progression	Date of last objective tumor assessment	Censored
Progression Documented on or between scheduled tumor assessments prior to treatment discontinuation 	Date of first objective tumor assessment showing objective progression	Progressed (Event)
Treatment discontinuation for undocumented progression	Date of last objective tumor assessment prior to discontinuation 	Censored
Treatment discontinuation due to toxicity or other reason	Date of last objective tumor assessment prior to discontinuation 	Censored
New anticancer treatment <28 days after discontinuation of treatment without progression	Date of last objective tumor assessment prior to new anticancer treatment	Censored
Death prior to first planned tumor assessment	Start date (C1D1)	Censored
Death without objective progression prior to treatment discontinuation 	Date of last objective tumor assessment prior to death	Censored
Progression after 2 or more missed tumor assessments	Date of last objective tumor assessment prior to the event	Censored

1: For censoring date, if a tumor assessment takes place over a number of days (eg, superficial lesions one day, scans another), the last date is used as the assessment date.

2: or within 28 days of discontinuation of treatment.

## DOSD and DOR

Censoring rules for DOSD and DOR will be the same as for PFS.

## Appendix 2. Categorical Classes for ECG and Vital Signs

### Categories for QTcB and QTcF

QTcB/QTcF (ms)	max. $\leq$ 450	450 $<$ max. $\leq$ 480	480 $<$ max. $\leq$ 500	max. $>$ 500
QTcB/QTcF (ms) increase from baseline	max. $<$ 30	30 $\leq$ max. $<$ 60	max. $\geq$ 60	

### Categories for PR and QRS

PR (ms)	max $\geq$ 300	
PR (ms) increase from baseline	Baseline $>$ 200 and max. $\geq$ 25% increase	Baseline $\leq$ 200 and max. $\geq$ 50% increase
QRS (ms)	max $\geq$ 200	
QRS (ms) increase from baseline	Baseline $>$ 100 and max. $\geq$ 25% increase	Baseline $\leq$ 100 and max. $\geq$ 50% increase

